A feasibility cluster randomised controlled trial of technology-assisted diabetes foot care in Pakistan- a study protocol.

Background

Diabetes is one of the most chronic diseases that affects millions of people worldwide. According to the International Diabetes Federation (IDF), the global prevalence of diabetes was 537 (10.5%) million in 2021, and it is estimated to reach 783 million (46%) by 2045. Around 75% of the diabetics live in lower-middle-income countries (1). Globally, Pakistan ranks 7th among the top ten countries with a high burden of diabetes. According to the International Diabetes Federation, approximately 19.4 million people in Pakistan have diabetes (2).

A severe chronic complication associated with diabetes is diabetic foot. Globally, the prevalence of diabetic foot is approximately 6.4%, and due to diabetes, every 30 seconds, an amputation is done, resulting in the loss of a lower limb or part of a lower limb. The pooled prevalence of diabetes foot ulcers in Pakistan is estimated to be 12.2% (3). The increase in the prevalence of diabetes and prolonged life expectancy of diabetics is leading to a further increase in the incidence of diabetic foot, with an estimated lifetime incidence of developing a foot ulcer as high as up to 25% (4-6). Of those diabetes patients who develop a foot ulcer, more than half are likely to die within five years (7). The treatment of diabetic foot ulcers is expensive and complicated, requiring long-term medication and/or hospitalization (8). Diabetic patients with foot ulcers incur five times higher health expenditure than those without ulcers. Therefore, to avoid the catastrophic health and financial implications of diabetic foot conditions, prevention and early treatment at the basic primary care level are required.

The World Health Organisation (WHO) guidelines for preventing and managing diabetic foot ulcers have emphasized the need for comprehensive foot care services, including screening, risk assessment, and patient education (9). In addition to these measures, the International Diabetes Federation (IDF) also emphasizes the training of healthcare professionals in managing and treating diabetic foot. People with diabetes should be educated about foot care, including regular foot examinations, proper footwear, and self-care techniques (10), which have proven to reduce the risk of amputation by 45-85% (11, 12). In addition, mobile applications have also been found effective in improving foot care knowledge and self-care (13).

In Pakistan's existing public health infrastructure, diabetes core care is available at the primary health centres and sub-district hospitals by the routine medical and allied staff. These publicly funded healthcare facilities provide their catchment populations free-of-cost services (i.e., clinical and diagnostic). The Directorate General Health Services and Association for Social Development, with the support of the World Diabetes Foundation, has successfully integrated a standardized diabetes-hypertension core care package in twenty districts of Pakistan. The NCD Program, considering the significant implications of the diabetic foot on the public health care system, has planned to integrate diabetic foot care in primary healthcare facilities, i.e., RHCs and hospitals. The Programme and the Association have developed products by adapting international best practice guidelines (14, 15). These guidelines and a context review informed the technical working group's development of the intervention package. These products were aimed to integrate diabetic foot care and improve patient engagement in diabetic foot care as well as behaviour or self-care practices.

Intervention Components:

- 1. Integrated foot care intervention design, i.e., staff roles and operational strategies to deliver integrated foot care and footwear components (given in Table 1).
- 2. Staff enabling package, i.e., training of doctors and allied staff
- 3. A flipbook (pictorial tool) for in-person patient counselling on footcare and suitable footwear
- 4. Mobile App for meaningful patient engagement in footcare and suitable footwear

Footcare tasks	Brief description/comments
Screening/ foot assessment: history and physical exam	A tailor-made screening tool for foot assessment
Educate/ counsel on footcare and footwear (in-person and mobile App.)	 Individual in-person counselling - using pictorial flipbook Mobile App.: download the App. on the patient's mobile, and educate them to access/ seek knowledge on footcare and footwear (pictorial and written with voice- over)
Access to suitable footwear and silicone rubber insoles/ orthotics	Footwear: • access to on-shelf suitable shoes in the market (for all)

 Table 1- Integrated Foot Care Intervention Components:

	o refer to a designated source of customized shoes (if						
	needed)						
	 Insoles – provision through project facilitation 						
Patients are to report footcare	Through the mobile App., the patients will be enabled to						
and footwear challenges and	report their care and social challenges, and these reported						
care delivery to respond to these	difficulties will be addressed through peer support						
challenges							
Periodic follow-up screening	Patient feet are to be screened periodically for foot						
and response (at RHCs)	condition (frequency subject to foot condition). The						
	patients get advised according to their foot condition.						
Digital referral for secondary	• Patients with foot ulcers, with(out) infection and/or						
care	necrosis, are to be referred for specialist care at DHQ						
	hospital.						
	• These patients (after specialist care at DHQ) will						
	continue getting follow-up care at their respective						
	RHCs.						
Staff maintain care records, and	• Diabetes footcare records are to be added to the patient						
the district monitors	card (for diabetics).						
performance	• Desk monitoring (EMR-based) is also supplemented by						
	periodic supervisory visits of the RHCs.						
Trial considerations:							
Trial enrolment	The facility staff inform the patient (per prescribed						
	protocol) and seeks their consent (to use their data in						
	trial results).						
	• If they consent – they will get enrolled in the trial.						
	• If they do not consent, they will be offered care as						
	per program guidance (without including in the trial)						
Outcome measurement (trial)	Data on foot care assessment and additionally on foot						
	care practices will be collected at the baseline and the						
	endline of study period.						
	-						

Aim

A well-designed RCT is required to test the effectiveness of this intervention package in diabetic foot care. Currently, there is insufficient data to inform the planning of a full-scale randomized controlled trial.

This feasibility trial will inform the design of a full RCT on technology-assisted diabetic foot care in primary healthcare facilities, i.e., RHCs.

Objective

To assess the feasibility of conducting a cluster randomized controlled trial comparing the effectiveness of the intervention package versus the routine care.

Methods

Study design

A pragmatic feasibility randomised controlled trial will be conducted comparing the contextualised intervention package with routine care. The study will start patient recruitment in July 2024 and complete end-line assessments in December 2024.

Eligibility

Inclusion Criteria

The study will recruit diabetes patients aged 25 or older registered for diabetes care at the primary health care facility, i.e., RHC. The age range has been kept broad to explore the outcomes across age ranges to inform a fully powered trial. As this is a pragmatic trial, participants will not be excluded based on comorbidities as the intervention would also cater to these groups when adopted on a large scale by the NCD Control Program. The patients will be included in the trial if written consent is obtained. The patients will also need access to a smartphone (i.e., personal smartphone or access to a smartphone within the household).

Exclusion Criteria:

Diabetes patients who plan to move out of the RHC catchment area during the study period will not be recruited in the trial. Those who refuse to give consent to participate will also be excluded.

Randomisation, Recruitment and Consent

Four districts will be randomized (i.e., two in each intervention and control arm). Two healthcare facilities will be randomly selected from each of the randomized districts. These RHCs will be sent a letter by the Directorate General Health Services (DGHS) to participate in the trial.

The diabetes patients at these facilities will be informed about the study objectives and the management and use of their data using an information sheet. The patients can ask questions to ensure they understand the project. A voluntary written consent will be obtained at the time of trial registration. The reasons for refusal will be noted. Patients who refuse to participate in the trial will receive the same program-recommended care, but their data will not be included in the trial. All patient records and personal information will be kept confidential to ensure privacy, and only healthcare providers and the project team will have access to these records. Recruitment of the

patients will be prospective. Each participant, once recruited, will be followed up for six months. Please see the Gantt chart at the end of the protocol for the study schedule.

Sample Size:

A formal size calculation is not required as this is a feasibility study. We have considered that collecting outcome data on approximately 320 patients (160 in each arm) would be sufficient to address our objectives. As this is a cluster-level trial, we estimate recruiting four districts (i.e., two districts per arm) with two randomly selected health facilities from each district. All health facilities are estimated to recruit 40 diabetic patients.

Intervention and Control Site Packages:

- At both intervention and control sites: Healthcare staff will be able to assess the diabetic foot and maintain records. This includes the provision of foot assessment-related materials (e.g., microfilament, tuning fork).
- At intervention sites, only:

Healthcare staff will be enabled to offer enhanced foot care and footwear intervention. The enabling includes contextualized implementation products: a) desk-guide for doctors; flip book for patient education; b) materials for foot care and footwear, e.g., silicone rubber insoles; c) digital mobile App. for patient engagement.

• At control sites:

Current footcare practices (as per individual physician discretion) will be continued, with an enhanced foot assessment and record keeping (as mentioned above). (Note: the enhanced assessment and record keeping will help ensure standardization and comparability of data between control and intervention arms).

Note: To keep the trial evidence relevant to the real-life program implementation processes, any special measure for enhanced staff adherence to the intervention protocol would be avoided.

Blinding

Blinding diabetic patients and healthcare providers will not be feasible, given the nature of the intervention. However, the data analysts will be kept blind to arm allocation.

Outcomes

The primary and secondary outcomes will be defined using the criteria of Thabane et al. (2010) for conducting feasibility studies (16) (outlined in Table 2).

Primary outcome:

The feasibility of clinical outcomes will be taken as the primary outcome.

Secondary outcomes:

The feasibility of operational and economic outcomes will be the secondary outcomes.

Indicators type	Quantitative Measures					
Clinical	• Uptake of recommended foot care behaviour (through Nottingham Assessment of Functional Footcare (NAFF))					
	• Quality of Life (through European Quality of Life 5 Dimensions 5 Level Version (EQ-5D-5L))					
	• Uptake of follow-up footcare visits (outputs)					
	• Uptake of suitable footwear/adherence to footwear (outputs)					
	• Uptake of mobile-App-assisted patient engagement					
	• Uptake of referral care at DHQ hospital					
	• Deterioration in foot condition/stage at the endline (in comparison with baseline)					
	• Complications during footcare (necrosis, amputation, hospitalization)					
Operational	 Patient enrolment – OPD load; diabetes patient load; refusal to participate in footcare intervention 					
	• Patient adherence to footcare follow-up (till endline)					
	• Staff – skill/ time/ support for the footcare tasks					
	• Availability of tools/ equipment for footcare tasks					
	• Availability of setting and arrangements for delivering footcare tasks					
	• Completeness of footcare data					
	• Validity of footcare data (matching from ≥2 sources)					
Economic	Providers' cost of:					
	• RHC enabling					
	• footcare per patient					
	• desired outcome (of footcare)					
	Additional emergency/catastrophic costs					

Table 2- Feasibility Outcome Indicators:

Data Collection

The health care staff will collect data on diabetic foot condition at baseline at the RHCs on the NCD patient record cards. The research team will conduct the surveys for patient foot care practices using the Nottingham Assessment of Functional Footcare and European Quality of Life 5 Dimensions 5 Level Version tools.

Statistical Methods

A descriptive analysis will be conducted based on the recommendations about good practices in the analysis of feasibility studies. These will be presented as means and SDs or 95% CIs, medians and IQR, or percentages. The trial will examine the effects of intervention during the analysis and use the data to inform estimates of a fully powered RCT.

Ethics

Ethical approval for this study has been obtained from the Research Ethics Board of the Association for Social Development (Ref- no: ASD-EAG-23-001). This study has been approved from The University of Oxford Research Ethics Committee (OxTREC Reference: 560-24).

There is no anticipated risk to trial patients during this study. A possible ethical concern could be that the control group will not receive the foot care intervention during the trial. However, this concern has been addressed by rolling out the intervention in the control clusters at the end of the study. Participants assigned to the control group will be placed on a waitlist. Upon completion of the study, the intervention components will be introduced to the control group, and the application will also be made available for download within the control clusters.

The patient data will be stored in accordance with the Data Protection Act 1998. The hard copy of patients' record will be kept in a lock, and all the patient's data will be pseudo-anonymised using a unique patient ID number for each participant. This pseudo-anonymised data will be saved on a secure, password-protected computer drive, which will only be accessible to the research team.

Strengths and Limitations

The trial will be conducted under routine programme circumstances with no additional resources required. The study will address an area which has minimal available evidence. However, blinding healthcare professionals and participants will not be possible due to the nature of the intervention.

Dissemination plan

The results of this study will be published in peer-reviewed journals. The protocol and project updates will also be available on the Open Science Framework. The study findings will be presented in as many research conferences at national and international level as possible. These findings will be disseminated in a workshop to all policymakers, i.e., Directorate General Health Services and Provincial NCD Disease Control Programmes. In addition, social media will be used to ensure the coverage of our findings.

Gantt Chart

Tasks	2024			2025							

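### Patients are recruited after district allocation by RHC staff who know their arm, and no rule fixes which eligible attendees are approached, so patient selection can differ by arm

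*Protocol*

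**What the plan says.** All references are to the Protocol.

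- **Allocation** (Randomisation, Recruitment and Consent): "Four districts will be randomized (i.e., two in each intervention and control arm".
- **Facilities** (same section): "Two healthcare facilities will be randomly selected from each of the randomized districts". Then: "These RHCs will be sent a letter by the Directorate General Health Services (DGHS) to participate in the trial". No step is given for an RHC that declines.
- **Who recruits** (Table 1, Trial enrolment): "The facility staff inform the patient" and seek consent for use of the patient's data in the trial results.
- **When** (Randomisation, Recruitment and Consent): recruitment of the "patients will be prospective". Sample Size expects 40 patients per facility.
- **Blinding**: "Blinding diabetic patients and healthcare providers will not be feasible, given the nature of the intervention". Only the data analysts are blinded.
- **Smartphone** (Inclusion Criteria): "The patients will also need access to a smartphone", either their own or one in the household. The criterion is the same for both arms.
- **Safeguards already present**: reasons for refusal are noted, and patients who refuse get the same programme care. Table 2 lists outpatient load, diabetes patient load and refusals among the operational indicators. Foot condition and foot care practices are measured at baseline, and the research team, not the facility staff, runs the NAFF and EQ-5D-5L surveys.
- **Use of the data** (Statistical Methods): intervention effects will be examined and the data will feed the estimates for a fully powered RCT.

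**The concern.** In a cluster trial, randomising districts balances the clusters only in expectation. It does not balance the patients if they are identified and approached later by people who know the arm. Staff at an intervention RHC have been trained in a new package and will have to deliver it. They may, without any intent to bias, approach patients who seem engaged, at ease with a phone or in particular need of foot care. Staff at a control RHC have no such reason and may approach whoever attends. This is a risk that the design leaves open; the document does not say that it happens.

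Three sets of results are exposed: enrolment and refusal, which are feasibility outcomes in their own right; NAFF and other behaviour measures; and deterioration in foot condition. If recruits differ by arm, an arm difference in any of these may partly reflect who was recruited. The full RCT would then be planned on it, and might inherit the same recruitment procedure.

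**Working it through.** **1. The design counts.** 4 districts × 2 RHCs × 40 patients = 320, and 2 × 2 × 40 = 160 per arm. Both agree with Sample Size. The point does not depend on them, and the fix does not change them.

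**2. Order of steps, read across sections.**

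| Step | What the protocol fixes | Can it depend on arm? |
|---|---|---|
| District allocation | Random, two per arm | No |
| RHC draw | Random within the randomised districts | Not by the draw itself |
| RHC participation | Letter after the draw; nothing on decliners | Yes, through acceptance or replacement |
| Whom to approach | Not fixed | Yes |
| Information and consent | Facility staff, not blinded | Yes |
| Analysis | Analysts blinded | Too late to affect enrolment |

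That RHCs are drawn after allocation is inferred from the reference to randomised districts. It is the plain reading. The protocol does not say that allocation is concealed until patients are enrolled, that patients are listed before allocation or taken consecutively, or that someone unaware of the arm recruits them.

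**3. What the recorded data can show.** Selection among eligible attendees has two stages: being approached, then consenting. Refusal reasons describe the second stage only. Patient load gives a count of diabetes patients, not of those eligible, those without a smartphone or those approached. The first stage, where staff discretion acts, is therefore not recorded.

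**4. Illustration.** The document gives no input for a size, so every input here is an assumption. Let half of the eligible patients be engaged. Let 80% of both groups be enrolled in control. In intervention, let 80% of engaged patients and a share c of the others be enrolled. The engaged share in intervention is

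0.5 × 0.8 / (0.5 × 0.8 + 0.5 × c).

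| c | Engaged share, intervention | Excess over control (50%) | Shift if engaged patients score 0.5 SD higher |
|---|---|---|---|
| 0.80 | 50.0% | 0 points | 0 SD |
| 0.70 | 53.3% | 3.3 points | 0.017 SD |
| 0.60 | 57.1% | 7.1 points | 0.036 SD |
| 0.50 | 61.5% | 11.5 points | 0.058 SD |

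The last column is the excess × 0.5 SD. In the last row about 98 of 160 intervention patients are engaged (0.615 × 160), against 80 in control, with no treatment effect. Recruiting more patients in the same way would not reduce this difference.

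**The case against.** The other side has real weight. This is a feasibility trial with a descriptive analysis, so no confirmatory test is at risk. Consent covers use of data only and refusers get the same care, so patients have no need to join the trial to obtain the package. That removes much of the usual motive for differential consent. Refusals and patient load are already recorded, and independent surveyors measure NAFF and EQ-5D-5L. All of this stands and lowers the stakes. None of it fixes whom the staff approach.

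Four stronger readings are tempting, and the document does not support them.

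- *Randomisation does not protect the facility sample.* A reader might infer this from the order of steps. But RHCs are drawn at random within each district, and such a draw favours neither arm whether it comes before or after allocation. Only acceptance or replacement after the letter could differ by arm. No replacement is described, and the letter comes from the health directorate.
- *Smartphone access is checked in one arm only.* Installing the App is an intervention task and is not described as an eligibility test. The protocol does not say that control staff omit a check.
- *The bias rivals the sampling error.* If 20% to 50% of one arm's recruits were selected with NAFF 0.5 SD higher, the shift would be 0.10 to 0.25 SD, against a half-width of 1.96 × √(2/160) = 0.219 SD. The shares and the 0.5 SD are not in the document, and the half-width ignores clustering, so it understates the uncertainty with two districts per arm. Even on these inputs, 0.10 SD is less than half of 0.219.
- *The bias could not be seen afterwards.* Baseline foot condition and foot care practices are measured, so some imbalance can be described. Differences in unmeasured traits cannot.

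**Conclusion.** The point holds for patient recruitment. Allocation comes first, unblinded facility staff recruit prospectively, and nothing fixes who is approached. The comparisons of enrolment, NAFF and foot condition are therefore open to arm-dependent selection, which analyst blinding does not prevent and the recorded data would show only in part. The facility step is a lesser point, confined to what happens after the letter, and rests on the plain reading of the order of steps.

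No magnitude follows from the document. The range of 0 to 11.5 percentage points shows only how the mechanism works under assumed enrolment rates. The change is worth making even in a feasibility trial, because enrolment is itself an outcome and the arm data will inform the full RCT.

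**What to change.** 1. In both arms, approach consecutive eligible registered attendees, or work through a random list from the diabetes register, until about 40 per RHC have consented. Ask the same smartphone-access question before consent in both arms.
2. Complete consent, baseline foot assessment, NAFF and EQ-5D-5L before any arm-specific counselling or App download.
3. Add to the refusal reasons already recorded the counts of patients eligible, without a smartphone, approached and refused at each RHC, and report them by arm.
4. Draw the RHCs and obtain their agreement before the district allocation is disclosed.

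The cost is a short log, a reordering of steps and less staff freedom over whom to approach. No extra staff are needed, and the sample stays at 320. The log would also give the full RCT its eligibility and consent denominators.

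### The number said to be sufficient with outcome data (about 320) equals the number to be recruited (an estimated 320), leaving no margin for loss over six months

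*Protocol*

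**What the plan says.** All the figures stand in the protocol.

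- **Size judged sufficient.** The Sample Size section waives a formal calculation because this is a feasibility study, then states that "collecting outcome data on approximately 320 patients (160 in each arm) would be sufficient to address our objectives".
- **Recruitment.** Under Randomisation, Recruitment and Consent, "Four districts will be randomized (i.e., two in each intervention and control arm". The Sample Size section repeats the structure, "two districts per arm) with two randomly selected health facilities from each district", and adds: "All health facilities are estimated to recruit 40 diabetic patients".
- **Duration.** "Each participant, once recruited, will be followed up for six months".
- **Timing of outcome data.** The last row of Table 1 places collection of foot assessment and foot care practice data at baseline and at the "endline of study period".
- **What the trial is to learn.** The operational rows of Table 2 include "Patient adherence to footcare follow-up (till endline" and the completeness of footcare data.

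The protocol states no expected loss to follow-up.

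**The concern.** The sufficiency statement refers to patients from whom outcome data are obtained. The recruitment plan refers to patients enrolled. In a six-month study with an endline assessment these are different quantities, and the first is normally smaller. Here they are the same number, so the outcome-data figure is fully met only if almost everyone recruited is assessed at endline. Yet the protocol treats follow-up to endline and data completeness as open questions.

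What is at stake is modest but practical. Under ordinary attrition the trial would fall short of the number its own protocol calls sufficient, and a reader could take that as a failure of feasibility. A clearer sentence now would avoid this. Whoever plans the full trial also needs to know which number 320 is: enrolled or analysed at endline.

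**Working it through.** **Inputs from the protocol**

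- Districts: 4, two per arm (Randomisation, Recruitment and Consent; Sample Size)
- Facilities per district: 2 (same sections)
- Patients per facility: 40, an estimate (Sample Size)
- Target with outcome data: about 320, 160 per arm (Sample Size)
- Follow-up: six months per participant (Randomisation, Recruitment and Consent)
- Loss to follow-up: not stated

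**Step 1. Reproduce the plan's figure.**

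Recruited = districts x facilities per district x patients per facility = 4 x 2 x 40 = 320.

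Per arm = 2 x 2 x 40 = 160.

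This matches the protocol's 320 and 160 exactly.

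**Step 2. Loss implied by the plan.**

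Implied loss = 1 - (target with outcome data / recruited) = 1 - 320/320 = 0%.

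**Step 3. Number left under an assumed loss d.**

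With endline data = 320 x (1 - d); per arm = 160 x (1 - d). The rates are assumptions, since the protocol gives none.

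| Assumed loss d | Total with endline data | Per arm |
|---|---|---|
| 5% | 320 x 0.95 = 304 | 152 |
| 10% | 320 x 0.90 = 288 | 144 |
| 20% | 320 x 0.80 = 256 | 128 |
| 30% | 320 x 0.70 = 224 | 112 |

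**Step 4. How much the word *approximately* can absorb.** The protocol sets no tolerance. If it is read as within 3% (an assumption), then 320 x 0.03 = 9.6, so up to 9 patients could be lost, leaving 311. A 10% loss is 32 patients and does not fit that reading.

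**Step 5. Which measures are affected.** Of the clinical indicators in Table 2, NAFF and EQ-5D-5L at endline need a completed endline survey, and deterioration in foot condition needs both a baseline and an endline assessment. These lose patients when follow-up is incomplete. Adherence to follow-up and use of the mobile App are naturally proportions of everyone enrolled. A patient who drops out still counts in those denominators, which stay at 320 in total and 160 per arm.

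**The case against.** The strongest defence is that the wording is loose on purpose. The outcome figure is approximate, 40 per facility is an estimate and not a cap, and nothing prevents a facility from enrolling more. The study disclaims formal sizing and plans a descriptive analysis. Patients who intend to leave the catchment area are excluded, which removes one foreseeable cause of loss. The research team carries out the NAFF and EQ-5D-5L surveys, so a missed care visit does not necessarily mean a missing outcome.

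Much of this stands, and it rules out several stronger readings that a reader might infer:

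- *That the plan guarantees exactly 320 and is bound to miss it.* The text estimates and approximates. *Unlikely to be reached* is as far as it supports.
- *That power or precision is overstated.* The protocol states no power, effect size or interval width, so there is no such claim to be wrong.
- *That estimates of retention or App uptake lose patients through dropout.* Their denominators are those enrolled (step 5).
- *That 320 is shown to be too few because of clustering.* The protocol gives no intracluster correlation, and any figure would rest on an assumed one. Districts, two per arm, are the randomised units, so a calculation that treats facilities as independent would not settle the question. It is also a separate matter from the mismatch between enrolled and assessed patients.

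The defence does not explain why the same paragraph gives one number for two quantities. An unseen statistical analysis plan might state an expected loss, but both figures stand in the protocol and the mismatch is in its own text.

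**Conclusion.** The point holds as an inconsistency between two figures in one paragraph. The estimated recruitment of 320 equals the approximately 320 patients wanted with outcome data, so the plan leaves no margin for loss over six months. For endline measures, an assumed loss of 10% to 30% would mean 288 down to 224 patients (144 down to 112 per arm) in place of 320 (160 per arm).

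The equality of the two figures is certain. The size of the shortfall depends entirely on the loss rate, which the protocol does not give and which the trial is meant to reveal. The consequence is limited to how many patients contribute to the descriptive endline results and how the sufficiency statement should be read. The absence of a formal sample size calculation is not a fault in a feasibility trial and is not part of this point.

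**What to change.** Amend the Sample Size paragraph in two sentences:

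1. Name 320 patients (160 per arm, about 40 per RHC) as the enrolment target.
2. State the smaller number expected with six-month outcome data, give the loss rate behind it, and say that this rate is an assumption which the trial will itself estimate. For example, 10% would give about 288 (144 per arm) and 20% about 256 (128 per arm). The sponsor should choose the rate.

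The judgement of sufficiency should then be attached to that smaller number, since it concerns data obtained and not patients enrolled.

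The cost is the wording change and a less favourable stated figure for endline data. Enrolment, sites, visits and analysis stay as they are.
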